Data collected at a baseline visit will include: subject demographics, disease history, comorbidities, vital signs, laboratory investigations, PGA, PASI and DLQI scores and serum levels of ADA. Subjects will continue to self-administer ADA (40 mg eow) but will have oral MTX added to their treatment at a dose to be defined by the Investigator. At site visits 8, 16 and 24 weeks after initiation of ADA/MTX, the following parameters will be assessed: physician assessment of disease status (using a satisfaction questionnaire); subject self-assessment of disease status (using a satisfaction questionnaire); PGA; PASI; DLQI; adverse events (AEs); serum levels of ADA.
Satisfaction questionnaire: Both Investigators and subjects will be asked how satisfied they are with the Ps control provided by the subject's current treatment. The provided responses will be: completely dissatisfied; moderately dissatisfied; slightly satisfied; highly satisfied; completely satisfied. Subjects with an Investigator assessment of completely or moderately dissatisfied with treatment will be categorized as a sub-optimal responder.
The 70-day safety follow-up period begins from the last dose of ADA. Subjects will be discontinued from the study if they withdraw consent or if they are deemed unsuitable to continue for any reason by the Investigator in consultation with the AbbVie Medical Monitor.

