### **Satisfaction with Treatment Evaluation**

Satisfaction with treatment will be assessed using a questionnaire similar to one developed by Christophers et al (28) for quantifying physician and Ps subject satisfaction with biologic therapy. In this study, dermatologists and subjects were surveyed regarding their satisfaction with therapy using the following questions:

Dermatologist survey question: Overall, at this point in time, how satisfied are you with the Ps control provided by the subject's current treatment regimen?

Subject survey question: Overall, how satisfied are you with your current treatment for Ps?

The same questions will be used in the present study. The response choices provided will be:

- Completely dissatisfied
- Moderately dissatisfied
- Slightly satisfied
- Highly satisfied
- Completely satisfied

Within the context of the study, Investigators indicating complete or moderate dissatisfaction with treatment will be combined to indicate subjects eligible for the study during screening (i.e., subjects with a sub-optimal response to ADA). Satisfaction with therapy will be defined by the combination of highly or completely satisfied responses. The questionnaires will be administered during screening and after 8, 16 and 24 weeks of ADA/MTX. Additional details of the questionnaire structure are provided in [Appendix C](#).

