**Satisfaction Questionnaire – Subject**

Overall, how satisfied are you with your current treatment for Ps?

- Completely dissatisfied
- Moderately dissatisfied
- Slightly satisfied
- Highly satisfied
- Completely satisfied

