10.0 Efficacy Analysis

10.1 General Considerations

Point estimates and 95% confidence intervals (CIs) based on normal approximation will be provided for the discrete efficacy variables such as the proportion of responders to ADA/MTX. Change and percent change from baseline variables will be estimated using an appropriate estimation from a Mixed Model and statistical tests of change from baseline equal to zero will be carried out at the 0.05 significance level; 95% confidence intervals will also be provided.

Descriptive statistics will be provided. These include the number of observations, mean, and standard deviation for continuous variables and counts and percentages for discrete variables. Baseline and visit means at each scheduled visit will also be provided for change and percent change from baseline continuous variables.

Missing data will be imputed using the following methods for the efficacy analyses:

- Non-Responder Imputation (NRI): The NRI analysis will categorize any subject who has missing value at a specific visit as non-responder (or "dissatisfied" in satisfaction variables) for that visit. NRI will be the primary approach in analyses of categorical variables.
- Mixed-effect Model Repeat Measurement (MMRM): A mixed-effect model will be developed for continuous endpoint repeated measured at Baseline, Week 8, 16, and 24; controlling for time and subject ID. The fixed effects will be used to report the visit means at corresponding visits. Change and percent

change from baseline will be determined accordingly. MMRM will be the primary approach in analyses of continuous variables.

- Last Observation Carried Forward (LOCF): The LOCF analyses will use the completed evaluation from the previous visit to impute missing data at later visits. Baseline efficacy evaluations will not be carried forward. LOCF will be a sensitivity approach in analyses of continuous variables and categorical variables.

All efficacy variables will be analyzed for the ITT population overall, and separately by primary sub-optimal responders and secondary sub-optimal responders at baseline.

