10.2.2 Secondary Efficacy Variables

Secondary efficacy variables included:

- Based on investigator assessment, the proportion of subjects achieving a satisfactory response at scheduled visits other than Week 16
- Based on subject self-assessment, the proportion of subjects achieving a satisfactory response at scheduled visits other than Week 16
- Proportion of subjects achieving PASI 50/75/90/100 at all scheduled visits

- Change and percent change from baseline in PASI at all scheduled visits.
- Proportion of subjects achieving a clinical response defined as a PGA of "Clear" or "Minimal" at all scheduled visits
- Change and percent change from baseline in DLQI at all scheduled visits
- Based on investigator assessment, the proportion of subjects at each of the five categories of satisfaction at all scheduled visits
- Based on subject self-assessment, the proportion of subjects at each of the five categories of satisfaction at all scheduled visits
- Proportion of subjects achieving a DLQI score of 0 or 1 at all scheduled visits
- Change and percent change from baseline in BSA at all scheduled visits.
- Change from baseline in hs-CRP at all scheduled visits.

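### The SAP imputes missing satisfaction ratings as dissatisfied in every categorical satisfaction variable, but the five-category tables have no cell for that value and would mix non-answers with real dissatisfaction

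*SAP*

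**What the plan says.** SAP 10.1 sets the rule: "The NRI analysis will categorize any subject who has missing value at a specific visit as non-responder (or 'dissatisfied' in satisfaction variables"). It then adds that "NRI will be the primary approach in analyses of categorical variables". LOCF is the sensitivity approach. No satisfaction variable is exempted.

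SAP 10.2.2 lists two secondary variables that display the whole scale: "Based on investigator assessment, the proportion of subjects at each of the five categories of satisfaction at all scheduled visits", and the matching item for the subject, "Based on subject self-assessment, the proportion of subjects at each of the five categories of satisfaction at all scheduled visits".

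The response options in the protocol synopsis are "completely dissatisfied; moderately dissatisfied; slightly satisfied; highly satisfied; completely satisfied". The forms in Protocol Appendix C offer the same five.

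On available versus imputed data, the documents differ:
- The protocol synopsis (Statistical Methods) applies the dissatisfied imputation to primary and secondary efficacy analyses. In the same paragraph it says that secondary outcomes are analysed on the data available at each visit.
- Protocol 8.1.4 repeats the imputation for primary and secondary analyses and keeps available data for additional exploratory outcomes.
- SAP 10.1 imputes and does not carry the available-data sentence.

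**The concern.** NRI suits a two-level endpoint. A missing form counts as not a responder, and there is only one such level to put it in. A five-level distribution is different. Its purpose is to show which opinions were held and how they moved over Weeks 8, 16 and 24, which bears on the secondary objective about size, timing and maintenance of benefit. Here the rule supplies a value that is not on the scale. A programmer must choose one of the two dissatisfied levels or create a sixth label, and neither document says which.

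If one of the two levels is chosen, a reader of the table cannot separate people who answered that they were dissatisfied from people who did not answer. In the investigator table, the opinion filled in is one the investigator never gave.

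**Working it through.** **The plan's own figures.** SAP 4.3 gives a 95% half-width of 13.9% at n=50 and a proportion of 50%. Check: 1.96 × √(0.5 × 0.5 / 50) = 13.86%, which agrees. All ten rows for n=50 and all ten for n=200 reproduce to rounding. These tables are sound and do not bear on this point; only n=50 is carried forward.

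**Two-level endpoint.** Protocol 5.3.1.1 says: "Satisfaction with therapy will be defined by the combination of highly or completely satisfied responses". Everything else, including *slightly satisfied*, is a non-response. A missing form treated as a non-responder therefore has exactly one place to go.

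**Five-level endpoint.** The imputed value is *dissatisfied*. The available levels are *completely dissatisfied*, *moderately dissatisfied* and three grades of satisfaction. No mapping is given.

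**Weight of one form.** 1/50 = 2 percentage points. SAP 10.1 also requires every efficacy variable separately for primary and secondary sub-optimal responders; in an assumed subgroup of 25, one form is 1/25 = 4 points.

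**Example (assumed: 10 of 50 missing, 3 observed *completely dissatisfied*).**
- Observed, ITT denominator: 3/50 = 6%.
- All missing forms placed in that cell: (3 + 10)/50 = 26%, which is 20 points higher.
- All placed in *moderately dissatisfied*: that cell gains 10/50 = 20 points and the *completely* cell stays at 6%.
- Kept as a sixth label: the five real categories sum to 40/50 = 80%.

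The share among those who answered is 3/40 = 7.5%. It has a different denominator and should not be set against 26%.

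**Range.** The documents give no missing-data rate and no expected distribution. Assume that, of the ratings given, 30% are at either dissatisfied level and 45% are highly or completely satisfied. With m forms missing and no bracketed gaps:
- dissatisfied under NRI = (0.30 × (50 − m) + m)/50
- dissatisfied as observed over ITT = 0.30 × (50 − m)/50
- responders = 0.45 × (50 − m)/50

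| Missing | Dissatisfied, NRI | Dissatisfied, observed | Missing row | Responders |
|---|---|---|---|---|
| 2 | 32.8% | 28.8% | 4% | 43.2% |
| 5 | 37.0% | 27.0% | 10% | 40.5% |
| 10 | 44.0% | 24.0% | 20% | 36.0% |
| 15 | 51.0% | 21.0% | 30% | 31.5% |

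The responder column is the same under either presentation.

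**Interaction with SAP 6.4.** When a visit is missing but ratings exist before and after it, SAP 6.4 uses the worse of the two, under NRI only. Take a subject with no Week 16 form who was rated highly satisfied at Weeks 8 and 24. Under NRI this subject is a Week 16 responder; in an observed-only table the subject is missing. Each such subject makes the top two rows fall 1/50 = 2 points short of the primary proportion.

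**The case against.** The strongest reply is that the rule was never meant for this table. The SAP gives *dissatisfied* in brackets as the satisfaction equivalent of non-responder. Protocol 8.1.4 names the rule after the sub-optimal responder, a class that pools both dissatisfied levels (Protocol 1.3). On that reading, only a clarifying phrase is missing. This is a fair account of the likely intent. It does not change the text, which covers categorical variables without exception, and a pooled class still does not identify a cell.

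Three stronger conclusions are tempting and are not supported.

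- *That no observed distribution will be produced.* SAP 10.1 separately promises counts and percentages for discrete variables, the synopsis has its available-data sentence, and the table layouts are in a separate document (SAP 13.0) that was not available here. The documents conflict; they do not show that observed data are excluded.
- *That dropout will appear as strong dissatisfaction.* This follows only if the *completely* cell is chosen, and the plan does not choose.
- *That the main result is distorted.* The two-level Week 16 endpoints treat missing as non-response, which is a usual conservative convention.

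Some features also limit how much is missing. Both questionnaires are scheduled at the Week 24 or early-termination visit (Protocol Table 1), termination procedures are due within 2 weeks of the last dose (Protocol 5.4.1), and the contiguous windows in SAP 6.4 assign such a rating to a visit. Bracketed gaps take a real rating, and SAP 8.0 tabulates discontinuations with reasons. All of this stands. It reduces the imputation without removing it: visits after an early termination stay empty, bracketing needs a later rating, LOCF also fills gaps, and disposition counts do not show which entries in a category are imputed.

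**Conclusion.** The point holds for the five-category satisfaction tables only. Followed as written, SAP 10.1 places non-answers in a distribution of opinions and names a value that the scale does not contain. Each missing form at n=50 moves 2 points into a dissatisfied level or outside the five categories. The 26% versus 6% example rests on two assumptions together: 10 of 50 forms missing, and all of them placed in *completely dissatisfied*. The true size cannot be derived from the documents, because they give no missing-data rate.

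These are secondary descriptive displays in a single-arm study and the primary endpoints are not affected, so the trial's main conclusion does not depend on this. It still needs settling before database lock, because the rule cannot be programmed for these tables without an unstated choice and the protocol and SAP disagree on the data to be used.

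**What to change.** - **SAP 10.1:** limit NRI for satisfaction to the two-level responder endpoints (highly or completely satisfied versus not). Leave the primary endpoints as they are.
- **SAP 10.2.2, five-category endpoints:** report observed counts in each category plus a separate Missing row, with the ITT number as denominator, so that the six rows sum to 100%.
- **SAP 6.4:** state whether the bracketing rule, now restricted to NRI, also applies to these tables. If it does, the top two rows can agree with the responder proportion. If it does not, footnote the difference.
- **Protocol synopsis and 8.1.4:** reconcile both with the SAP, since they give different rules for secondary outcomes.

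The cost is a small wording change in both documents and one added row per table. No new data are needed.

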10.2 Efficacy Variables

10.2.1 Primary Efficacy Variable

The primary efficacy endpoints will be:

- Based on investigator assessment, the proportion of subjects achieving a satisfactory response at Week 16 (satisfactory response is defined as highly or completely satisfied with therapy based on responses to the satisfaction questionnaire).
- Based on subject self-assessment, the proportion of subjects achieving a satisfactory response at Week 16 (satisfactory response defined as highly or completely satisfied with therapy based on responses to the satisfaction questionnaire).

10.2.2 Secondary Efficacy Variables

Secondary efficacy variables included:

- Based on investigator assessment, the proportion of subjects achieving a satisfactory response at scheduled visits other than Week 16
- Based on subject self-assessment, the proportion of subjects achieving a satisfactory response at scheduled visits other than Week 16
- Proportion of subjects achieving PASI 50/75/90/100 at all scheduled visits

- Change and percent change from baseline in PASI at all scheduled visits.
- Proportion of subjects achieving a clinical response defined as a PGA of "Clear" or "Minimal" at all scheduled visits
- Change and percent change from baseline in DLQI at all scheduled visits
- Based on investigator assessment, the proportion of subjects at each of the five categories of satisfaction at all scheduled visits
- Based on subject self-assessment, the proportion of subjects at each of the five categories of satisfaction at all scheduled visits
- Proportion of subjects achieving a DLQI score of 0 or 1 at all scheduled visits
- Change and percent change from baseline in BSA at all scheduled visits.
- Change from baseline in hs-CRP at all scheduled visits.

10.3 Handling of Multiplicity

No multiplicity adjustment will be applied to the efficacy analyses.

10.4 Efficacy Subgroup Analyses

PASI 50/75/90/100 endpoints will also be analyzed in the following subgroup:

- Subjects on ADA 40 mg eow prior to baseline or 40 mg once weekly prior to wash-out.

11.0 Safety Analysis

11.1 General Considerations

Safety analyses will include reporting of adverse events, laboratory, and vital sign measurements. Safety analyses with group comparison will be carried out using the Safety Population.

Mean changes from baseline in all continuous laboratory parameters and vital signs variables to post-baseline visits will be summarized for the Safety Population. No

statistical tests will be applied. The number of non-missing values will be given. Missing safety data will not be imputed.

11.2 Analysis of Adverse Events

Treatment-emergent adverse events (TEAEs) will be tabulated.

Adverse events that start more than 70 days after the last study ADA injection during the study will not be included in the summaries; however, if reported, these adverse events will be included in the adverse event data listings. A summary of all pretreatment (i.e., event start date is prior to the date of the first study drug injection) serious adverse events will be provided. Adverse events will be summarized by patient year as well.

11.2.1 Treatment-Emergent Adverse Events

Treatment-emergent adverse events (TEAE) are defined as following:

TEAEs are defined as any event with an onset date that is on or after the maximum date of either the first dose of study ADA or the first dose of MTX and no more than 70 days after the last study ADA injection during the study.

If an incomplete onset date is collected for an adverse event, the event will be assumed to be treatment-emergent unless there is other evidence that confirms that the event is not treatment-emergent (e.g., the event end date is prior to the study drug start date).

Adverse event data will be summarized and presented using the Medical Dictionary for Drug Regulatory Activities (MedDRA[®]) system organ class (SOCs) and preferred terms (PTs).

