- m. Documentation from the physician that the subjects are not known to be HIV positive, or at risk for HIV risk factors, will be sufficient. HIV testing is not required unless, in the opinion of the Investigator, it is warranted. A subject will not be eligible for study participation if documentation indicates a positive HIV infection. AbbVie will not receive results from any HIV testing and will not be made aware of any positive result
- n. All females of childbearing potential will have a serum pregnancy test at Screening
- o. All females of childbearing potential will have a urine sample performed locally at Baseline prior to study enrollment, at week 8, 16 and study discontinuation/completion. Any subject with a positive urine pregnancy test must have a negative serum test performed at the central laboratory prior to enrollment or continuation in the study
- p. Wash out procedure for subjects on 40 mg once weekly; these subjects should be started on ADA 40 mg eow for at least 8 weeks prior to study enrollment
- q. All AEs reported from the time of study drug administration until 70 days following last study drug injection will be collected
- r. SAEs will be collected from the time the subject signed the study-specific informed consent form until 70 days following last study drug injection
- s. Last dose of MTX will be taken on Week 23 and last dose of ADA will be taken at Week 22. Drugs will not be dispensed at Week 24
- t. Subjects should continue to receive adalimumab every other week during the screening period (if applicable) and the Baseline visit should coincide with the next planned dose of ADA.

---

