**5.5.4****Selection and Timing of Dose for Each Subject**

Subjects should take study medication as outlined in Section [5.5.1](#).

The kit number(s) to be dispensed, both for ADA and MTX, will be assigned by the IVRS/IWRS. Each ADA carton and MTX bottle will contain a unique number that is assigned to a subject via IVRS/IWRS. The number of kits dispensed will be managed by the IVRS/IWRS. On dosing days that occur on study visit days, subjects will administer ADA drug injection in the office under guidance of study site personnel after all specified study tests and procedures have been completed. Although subjects should be familiar with sterile subcutaneous injection technique, qualified study site personnel should directly observe subject self-injection at the time of all scheduled visits to ensure that it is carried out correctly. Site personnel observation of the subject's self-injection technique is of particular importance during the Baseline Visit. This supervision will serve as a confirmation of the use of safe and appropriate drug injection techniques and to answer any questions related to drug administration. ADA doses that do not occur on study visit days should be administered to subject by himself/herself, or by a designee (friend, family member or health care professional) throughout the study. For MTX, subjects should be instructed to bring their drug with them on study visit days that coincide with subject's MTX dosing schedule so that MTX can be taken in the office. Again, qualified study site personnel should observe oral MTX dosing, particularly to ensure that the correct number of tablets are taken for the prescribed MTX dose.

Each subject's dosing schedule should be closely monitored by the site at each study visit by careful review of the subject's dosing diary. This will ensure that all subjects enrolled into the study maintain their original ADA dosing schedule beginning with the first dose of study medication (Baseline/Day 0). Doses of ADA should be taken on the same "scheduled dosing day" of each appropriate dosing week. Dosing schedule for MTX should also be closely reviewed to ensure that drug is taken at the required dose per week and, if the weekly drug dose is split (i.e. > 10 mg/week), that the dose is taken on the same day in two equal doses. In addition, dosing diaries should be reviewed to ensure that the subject has adjusted dosing to reflect any study-related MTX dose increases.

---

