### **8.1.1 Analysis Population**

The intent-to-treat (ITT) population will be used in the assessment of treatment satisfaction and in the evaluations of ADA + MTX efficacy. The ITT population is defined as:

- All subjects who received at least one dose of ADA and one dose of MTX.

A per protocol population will not be defined for this qualitative study.

The safety population is defined as all subjects who received at least one dose of ADA and one dose of MTX and will be used to evaluate safety of ADA + MTX.

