**8.1.5 Statistical Analysis of Safety**

All AEs, SAEs, and AEs leading to discontinuation will be collected during the study and up to 70 days after the last dose of ADA. Safety analyses will be carried out using the Safety Population. A treatment-emergent AE is defined as an event with onset or worsening after the first dose of study drugs (ADA + MTX) and within 70 days after the last dose of ADA. The number and percent of subjects experiencing treatment-emergent AEs will be tabulated using the Medical Dictionary for Drug Regulatory Activities (MedDRA®) system organ class and preferred term. Summaries (including percentages and event per 100 patient-years) of SAEs, deaths and AEs leading to discontinuation from the study will be provided as well.

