5.0 Analysis Populations

5.1 Definition of Analysis Populations

Intent-to-Treat (ITT) Populations

The Intent-to-Treat population will be used for all efficacy analyses, which is defined as all subjects who receive at least one dose of study ADA and at least one dose of MTX during the study.

The primary efficacy analyses will also be conducted for the following sub-populations:

- ITT Subjects who are defined as primary sub-optimal responders at baseline based on Investigator assessment.
- ITT Subjects who are defined as secondary sub-optimal responders at baseline based on Investigator assessment.

Safety Populations

The Safety Population will be used for all safety analysis, which is defined as all subjects who received at least one dose of study ADA and one dose of MTX during the study. In this study, the safety population is the same as the ITT Population.

Notations for Treatment Groups

- ADA/MTX: Subjects who received ADA and MTX as study drugs.

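### If the two study drugs start on different days, the SAP's safety start rules leave some collected adverse events out of every summary table and label others pretreatment

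*SAP*

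**What the plan says.** **TEAE window.** SAP Section 11.2.1 starts it "on or after the maximum date of either the first dose of study ADA or the first dose of MTX" and ends it "no more than 70 days after the last study ADA injection during the study".

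**Pretreatment events.** The one planned summary of events outside that window is of pretreatment SAEs. SAP Section 11.2 defines these by "event start date is prior to the date of the first study drug injection". ADA is the only injected study drug.

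**Safety set.** SAP Section 5.1 takes "all subjects who received at least one dose of study ADA and one dose of MTX during the study" and states that this equals the ITT Population. Protocol Section 8.1.1 agrees: "The safety population is defined as all subjects who received at least one dose of ADA and one dose of MTX". The Safety paragraph of the synopsis and Section 5.3.4 repeat the both-drug rule.

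**Protocol TEAE definition.** Section 8.1.5 has "an event with onset or worsening after the first dose of study drugs (ADA + MTX) and within 70 days after the last dose of ADA". It does not say whether the clock starts with the first of either drug or once both have been taken.

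**Collection.** A footnote to Table 1 in Protocol Section 5.3.1 says: "All AEs reported from the time of study drug administration until 70 days following last study drug injection will be collected".

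**Dosing plan.** Protocol Section 5.5.1 has the first pen injected at the site at Baseline, and Appendix H has the first MTX dose taken in clinic at the same visit.

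**Date conventions.** SAP Sections 6.1 (baseline), 6.3 (Rx Day 1) and 7.3 (prior and concomitant medication) use the later of the two first doses. Tables 5 and 6 in Section 6.4 count days from each drug's own first dose.

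**The concern.** The safety boundaries do not meet. The pretreatment period ends at one date, the treatment-emergent period begins at another that may be later, and the safety set requires both drugs. An event that falls between the two first doses is collected, but most such events have no table to go to. A subject who has an event after one drug and never takes the other is removed from the safety set together with that event.

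MTX is the drug being added, and Protocol Section 3.2 names its added risk as the safety consideration. An early reaction to MTX that stops a subject from going on is an event a safety table should show. With about 50 subjects, one omission is visible.

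**Working it through.** The plan gives no figure for this point, so there is nothing to reproduce. The check applies the SAP's rules to a test event and then sizes the gap.

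**Step 1: classify a test event.** Take an event with a complete onset date on day 3, counting the first study drug dose received as day 0. Where both drugs are taken, the second starts on day 0 or on day 7 (the 7 days is an assumption). The tests are:
- TEAE tables: both drugs taken, and onset on or after the later first dose.
- Pretreatment SAE summary: serious, and onset before the first ADA injection.

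| Dosing order | Non-serious event | Serious event |
|---|---|---|
| Both on day 0 | TEAE tables | TEAE tables |
| ADA day 0, MTX day 7 | No table | No table: 3 is not before 0 and is before 7 |
| MTX day 0, ADA day 7 | No table | Pretreatment SAE summary: 3 is before 7, though MTX was taken on day 0 |
| ADA only | Outside safety set, no table | Outside safety set, no table |
| MTX only | Outside safety set, no table | Outside safety set, no table |

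If the pretreatment cut-off were read loosely as the first dose of any study drug, the MTX-first SAE would also reach no table.

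**Step 2: exits from the gap.** Three provisions catch some of these events:
- SAP Section 11.2.1 assumes an event with an incomplete onset date to be treatment-emergent unless other evidence shows that it is not.
- Protocol Section 6.1.1.1 has worsening of a reported AE recorded as a new AE, which can then fall inside the window.
- SAP Section 11.2.1.6 lists SAEs, deaths and AEs leading to discontinuation of study drug. The sentence carries no treatment-emergent limit, although it sits under the TEAE heading.

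**Step 3: size of the gap.** Planned exposure by the SAP Section 9.0 formulas is last dose minus first dose, plus 14 days for ADA or 7 days for MTX:
- ADA: 22 × 7 + 14 = 168 days
- MTX: 23 × 7 + 7 = 168 days

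The documents give no expected gap. For assumed gaps, the share of an affected subject's planned exposure is:

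| Gap (days, assumed) | Gap / 168 |
|---|---|
| 1 | 0.6% |
| 3 | 1.8% |
| 7 | 4.2% |
| 14 | 8.3% |

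**Step 4: event rates.** SAP Section 11.2.1.8 divides the number of TEAEs by summed study drug exposure, without saying whether that is ADA, MTX or combined exposure. Exposure to the earlier drug runs from its own first dose, so gap days can enter the denominator while their events are left out of the numerator. The denominator effect is slight. With 50 subjects fully exposed, the total is 50 × 168 / 365.25 = 23.0 patient-years, and one 7-day gap contributes 7 / 365.25 = 0.019, or 7 / 8,400 = 0.08% of it. What matters is the missing event.

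**Step 5: single-drug subjects.** Each is 1/50 = 2% of the target enrolment.

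**The case against.** **The planned gap is zero.** This stands. Both first doses belong to the Baseline visit, and a later-date rule with separate drug clocks may be no more than a programming convention. It does not show that gaps are expected.

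**A reader might infer from Protocol Section 5.5.4 that the first MTX dose may be delayed,** because subjects are to "bring their drug with them on study visit days that coincide with" their MTX schedule. The text does not support that. MTX is first dispensed at Baseline, so there is none to bring to that visit. The sentence fits later visits.

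**A reader might also infer that every event between the two first doses is lost, SAEs included.** That is too strong. An MTX-first SAE is mislabelled, not lost, and the provisions in Step 2 of the working catch some of the rest. SAP Section 11.2.1.1 also leaves room for extra tabulations.

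**The rule isolates combination exposure.** This is the best defence of the design. Subjects enter on ADA and continue it through screening, so in the ADA-first case a gap event arises on the treatment they already had. It is reasonable not to attribute that event to the combination, though not a reason to tabulate it nowhere. In the MTX-first case the defence fails. Such a subject, already on ADA, is on the combination from the first MTX dose, whether or not the first study pen has been used.

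**The SAP follows the protocol.** For the safety set it does, and there is no contradiction to report there. For the TEAE start, Protocol Section 8.1.5 is compatible with the later-date rule but does not require it.

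**Conclusion.** The point holds in a limited, conditional form. If both drugs start on the same day in every subject, nothing is affected. If they do not, four consequences follow from the SAP as written:
- Non-serious gap events with complete onset dates, and gap SAEs when ADA came first, reach no summary table.
- Gap SAEs when MTX came first are presented as pretreatment.
- Subjects who receive only one study drug, and their events, are outside the safety set.
- Gap days can count as exposure while their events do not count.

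The number of subjects affected cannot be derived from the documents. The gap lengths used here are assumptions, and the 2% describes one subject, not a forecast. The documents do not support a claim of systematic event loss. This is a minor defect, worth correcting because the correction is nearly free.

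**What to change.** Make these changes before database lock:
- **Safety Population:** at least one dose of either study drug.
- **TEAE start:** the earlier of the two first doses.
- **Pretreatment:** onset before that same date.
- **Patient-years:** start the clock there too, and state which exposure is summed.
- **TEAE end:** the present limit counts from the last study ADA injection, which an MTX-only subject does not have. State the limit for such subjects. The collection period in Protocol Section 6.1.4, which runs 70 days from discontinuation of study drugs, is one already in the documents.
- **Rx Day and safety baseline:** SAP Sections 6.1 and 6.3 use the later date, so gap TEAEs would carry negative Rx Days and a safety baseline could be measured after the first drug. State how both are handled.
- **Matching text:** remove the statement in SAP Section 5.1 that the safety set equals ITT, and align the Safety paragraph of the protocol synopsis and Protocol Sections 5.3.4, 8.1.1 and 8.1.5.

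Keep the both-drug ITT set for efficacy. If the sponsor prefers a TEAE definition tied to the start of the combination, the alternative is a separate table of gap events and of events in single-drug subjects.

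No new data are needed. The cost is small wording and programming changes, and the safety and ITT sets may differ by a few subjects.
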